8.1. General Methods

Statistical methodology and analyses are in accordance with the principles outlined by the International Conference on Harmonization (ICH) E9 guidelines. Statistical analyses will be carried out by using SAS Version 9.4 or higher. Any deviations from the planned analysis as described in the SAP will be justified and recorded in the clinical study report.

Patient listings of all data in the database will be provided, including data collected in the eCRF as well as data transferred electronically (e.g., lab data). All data listings that contain an evaluation date will contain a relative study day. Pre-treatment and on-treatment study days are numbered relative to the day of the first dose of study medication, which is designated as Day 1. The listings will be presented based on the respective analysis population set and sorted by cohort, treatment group, patient number, and assessment date and time (if applicable).

Tabulations will be produced for appropriate demographic, baseline, safety, efficacy and PK parameters. For continuous variables, absolute values and change from baseline (if applicable) will be summarised by reporting the number of observations (n), arithmetic mean, standard deviation (SD), median, minimum, and maximum.

Categorical data will be summarised using number of observations (n), and frequency and percentages (%) of patients. The categories in the summary will follow the logical ordering on the eCRF page, with the 'Other' category displayed after all other pre-specified categories. If the calculation of percentages include patients with missing values, a 'Missing' category is displayed last. The number of patients per treatment group and overall (in a 'Total' column) will be used as the denominator for percentage calculations, unless stated otherwise in the table shell. All percentages will be rounded to one decimal percentages between 0.1% and 100%, inclusive, unless otherwise specified. Percentages equal to 100.0 will be presented as 100% and no percentages will be presented in case of frequencies of zero.

Only scheduled time points will be presented in summary tables. Data from unscheduled time points will be listed only. Tables will be presented by treatment group (and Total if applicable) as presented in Table 7. All header conventions are detailed in Section 16.2.4.

Table 7: Example of study phase and dose level presentation in TLF Shells

REC 0/0559 0.5	REC 0/0559 2.5	REC 0/0559 5.0	Vehicle	Total
μg/day	μg/day	μg/day	(N=xx)	(N=xx)
(N=xx)	(N=xx)	(N=xx)		

Adverse events, medical history, prior surgeries/procedures and ocular interventions terms will be coded for summarisation using the Medical Dictionary for Regulatory Activities (MedDRA® Version 22.1 or later). Prior and concomitant medications, will be coded using the World Health Organization (WHO) Drug Dictionary (September 2019 version).

8.2. Key Definitions

Baseline and change from baseline:

The baseline value will be defined as the last available measurement before the first administration of study treatment.

Change from baseline = (post-baseline value – baseline value).

Percentage change from baseline = (change from baseline / baseline value) * 100

Study day:

The study day is calculated relative to the day of first study drug administration, i.e., the first day of study drug administration is designated as Day 1. The day after is Day 2 and so forth until end of study (EOS). The preceding day to Day 1 is designated as Day -1, the day before Day -1 is Day -2, etc.

Calculation of duration

Applicable for adverse events, medical history, and concomitant medication.

If times are available and if the duration is less than 24 hours, the duration will be calculated as (end date/time – start date/time) and presented in hh:mm. If at least 1 time is missing or if the duration is at least 24 hours, it will be calculated as (end date - start date) + 1 and presented in days.

In case of partial/missing start or end date, duration will not be calculated.

8.3. Handling of Missing Data

All missing or partial data will be presented in the patient data listing as they are recorded on the eCRF. In general, partial or completely missing dates will not be imputed.

8.3.1. Handling of Missing or Partial Dates

The following rules apply for medications and procedures to determine if they are concomitant in case of partial or completely missing dates:

In a case where a medication, surgery, or procedure has the day of the start date missing but the start month and year are complete, it will be excluded as being concomitant only if the start month/year is before the month/year of study drug administration and if the stop date (either full date, month and year if missing day, or year if missing month and day) is before study drug administration. If the start day and month are missing but the start year is complete, a medication, surgery or procedure will be excluded as concomitant only if the start year is before the year of study drug administration and if the stop date (either: full date, month and year if missing day, or year if missing month and day) is before study drug administration.

The following rules apply to AEs with partial or completely missing dates to determine if they occurred during the treatment administration study period:

If the start day is missing but the start month and year are complete, an AE is not considered as a treatmentemergent AE (TEAE) only if the start month/year is before the month/year of study drug administration or if the stop date/time is before first treatment administration. If the start day and month are missing but the start year is complete, an AE is not considered as TEAE only if the start year is before the year of treatment administration or if the stop date/time is before first treatment administration. If the start date is completely missing, an AE will be considered as TEAE unless the stop date is before first treatment administration.

For the calculation of time since first NK diagnosis, partial dates are imputed as follows: if only month and year are available, the day = 15 will be assumed. If only year is available, month = 6 and day = 15 will be assumed. In case the imputed date is greater than the date of signed informed consent (IC), then the date of IC will be used as date of first NK diagnosis.

Missing visits or assessments and protocol deviations due to COVID-19 will be summarised and listed (Section 9.2.3).

8.3.2. Handling of Missing Data for the Primary, Secondary, Other and Exploratory Efficacy Endpoints

Missing efficacy assessment data due to intercurrent events will be handled according to the strategies as described in the estimand Section 7. All efficacy analyses using the primary estimand framework for definitions of ICEs and the strategies to deal with them, will be imputed via single value imputation, i.e. as failure/non-responder or LOCF.

For all parameters that need to be imputed using multiple imputation, ranges (minimum and maximum values) and decimal rounding will be specified as applicable. In total 20 imputed datasets will be created per parameter and visit (proc mi).

All intermittent missing efficacy assessment data will be multiple imputed under MAR assumption using a Markov Chain Monte Carlo (MCMC) approach for all endpoints where MI is required.

Once the monotone missing data pattern is obtained the remaining missing values (whether missing due to ICE or not) will be imputed. Missing efficacy assessment data that are missing without the definition of an ICE met, will be multiple imputed under MAR assumption with either a monotone linear regression for continuous parameters or monotone logistic regression for categorical parameters, as applicable. Treatment group and randomisation strata will be included.

For the supplementary estimand strategy and first sensitivity analysis of the primary endpoint as well as for the continuous secondary efficacy endpoints multiple imputation will be applied for missings due to intercurrent events as follows:

- MNAR: multiple imputation will be performed based on the assumption of MNAR with a controlbased pattern approach and vehicle as reference group. Randomisation strata will be included. Categorical parameters will be imputed using a monotone logistic regression and continuous parameters will be imputed with monotone linear regression, as applicable.
- MAR: multiple imputation will be used to impute continuous parameters with monotone linear regression and categorical parameters with monotone logistic regression, as applicable. Treatment group and randomisation strata are included.
- Composite strategy: efficacy assessments that are not performed because of treatment discontinuation due to death will be imputed with worst value or failure/non-responder single imputation approach.

After the multiple imputation is completed, any necessary derivations, e.g. calculation of change from baseline, percentage change from baseline or categorisation of responders/non-responders based on an imputed continuous parameter, will be derived. Then the statistical tests as per efficacy endpoint (i.e., CMH test, ANCOVA) will be performed on all 20 imputed datasets per parameter. The ANCOVA results will be summarised directly by Rubin's rules (proc mianalyze) and presented in the summary tables. For the CMH test results the Wilson-Hilferty transformation (Wilson & Hilferty 1931) will be applied before combining the results by Rubin's rules. Odds ratios (OR) based on the 20 imputed datasets will be combined by Rubin's rules with the standard errors calculated based on the confidence intervals (CI) and log-transformation will be applied. Back-transformed results for OR will be presented in the tables.

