- Serum tears (should be stopped before the Screening Visit and are not allowed during treatment period)
- Topical ophthalmological treatments other than the study drugs provided by the study Sponsor and those listed below (Allowed Concomitant Therapies) are not allowed during the study including anti-viral topical and tetracycline ophthalmic treatment
- Botox (botulinum toxin) injections for pharmacological blepharoptosis

Allowed Concomitant Therapies

Topical ophthalmological treatments approved to be used during the study are:

- Preservative-free artificial tears (it is recommended to maintain a stable regimen during the study)
- Preservative-free topical antibiotics except topical tetracycline (if preservative-free antibiotic drops are not available, it is highly recommended to administer antibiotic drops with preservatives not more than once daily)
- Preservative-free anti glaucoma eye drop treatment only if administered maximum once daily as a single-agent treatment and at a stable regimen 4 weeks before screening and at the same dose during the study
- If possible, it is recommended to avoid formulations containing phosphate compounds

Administration of any other topical treatments in the eye is recommended to take place at least 1 hour before or after REC 0/0559 administration (and should not be administered less than 15 minutes before or after REC 0/0559).

Preventive anti-viral systemic treatment for herpes simplex virus (oral) is allowed (on a stable basis).

Generally, drugs needed to treat diseases causing NK (eg, diabetes) should be continued as required to ensure an appropriate treatment of the background disease.

COVID-19 vaccines will be considered as a concomitant medication and will be reported in the eCRF as described below.

Any medication or therapy that is taken by or administered to the patient during the course of the study must be recorded in the eCRF. The entry must include the dose, regimen, route, indication, and dates of use.

9.6.2 **Rescue Medications**

Anytime during the study, investigator can initiate a rescue treatment if clinically required (eg, if the disease worsens). Study drug should be discontinued. The rescue treatment will be decided by the investigator according to clinical judgment and may consist of topical, oral or surgical treatment. Rescue treatment will not be supplied by the Sponsor.

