9.5.2. Concomitant Medication

Concomitant medication will be coded using the WHO Drug Dictionary, and patient incidence will be summarised and tabulated by ATC Level 2 and 3 term and preferred term by treatment group and overall based on the mITT population. Patients will be counted only once for each ATC term or preferred term in the event that they have multiple records of the same ATC term or preferred term in the database. If a concomitant medication is used to treat an AE, the AE number will be presented in the prior and concomitant medication listing. If the concomitant medication is related to the medical history, the medical history number will be listed as well. The same applies if the use of concomitant medication is related to any ocular intervention or surgery or procedure then the respective event number will be displayed in the listing for reference.

A concomitant medication is defined as taken between the date of first dose of treatment and the date of last dose of treatment.

Any medication missing both start and stop dates or having a start date prior to the first treatment administration and missing the stop date or having a stop date on or after the last treatment administration and missing start date will be counted as concomitant. If only partial dates are available the approaches described in Section 8.3 are used to determine if a medication is concomitant.

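### SAP 8.3.1 counts a medication as concomitant despite a known stop before first dose when its partial start date falls in the month or year of first dose

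*SAP*

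**What the plan says.** SAP section 8.3.1 decides whether a medication, surgery or procedure with an incomplete start date is concomitant.

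- Day missing, month and year known: the record is "excluded as being concomitant only if the start month/year is before the month/year of study drug administration and if the stop date" is before dosing as well.
- Day and month missing, year known: the record "will be excluded as concomitant only if the start year is before the year of study drug administration and if the stop date" is before dosing as well.

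In both rules the stop date may be a full date, a month and year, or a year, so fully known stop dates are covered.

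SAP section 9.5.2 gives the definition: "A concomitant medication is defined as taken between the date of first dose of treatment and the date of last dose of treatment". It sends partial dates back to section 8.3. Sections 9.5.3 and 9.5.4 do the same for ocular interventions and for other surgeries and procedures.

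For adverse events, section 8.3.1 joins its conditions differently. With only the start year known, an event is "not considered as TEAE only if the start year is before the year of treatment administration or if the stop date/time is before" the first administration. A stop before first dose is therefore enough on its own.

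For a medication with no start date, section 9.5.2 says that one "having a stop date on or after the last treatment administration and missing start date will be counted as concomitant".

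**The concern.** A medication that ended before first dose cannot have been taken between first and last dose, whatever its start date. A worst-case rule should settle what is unknown. Here the date that decides the question can be known, and the rule sets it aside because another date is incomplete.

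The situation is plausible in this trial. Inclusion criterion 4 requires no improvement over the two weeks before Screening despite conventional treatment, and it names serum tears and therapeutic contact lenses. Protocol section 9.6.1 then says "Serum tears (should be stopped before the Screening Visit and are not allowed during treatment period"), and Screening runs from Day -3 to Day 1. Therapy that is prohibited on study and was stopped just before dosing is to be expected. If its start date is incomplete, it can be summarised by arm as used during treatment.

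**Working it through.** There is no figure in the plan to reproduce. The check applies the rule literally and compares the result with the 9.5.2 definition.

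**Rules compared**

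- Section 8.3.1: not concomitant only if (partial start earlier than the month or year of first dose) AND (stop < first dose).
- Section 9.5.2: not concomitant if stop < first dose.
- Adverse-event form, for comparison: excluded if (partial start earlier) OR (stop < first dose).

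**Worked dates, first dose 20 June 2022**

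| Recorded start | Stop | 8.3.1 | 9.5.2 definition | 'Or' form |
|---|---|---|---|---|
| June 2022 | 17 June 2022 | concomitant | not | not |
| 2022 | 17 June 2022 | concomitant | not | not |
| May 2022 | 17 June 2022 | not | not | not |
| 2021 | 17 June 2022 | not | not | not |
| May 2022 | 30 June 2022 | concomitant | concomitant | not |

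Rows 1 and 2 are the error. Rows 3 and 4 show its limit: an earlier partial start with a pre-dose stop is handled correctly. Row 5 shows why the adverse-event 'or' cannot be copied. Treatment emergence depends on onset, whereas concomitant use depends on the whole interval, so 'or' would drop a therapy begun earlier and still in use on treatment.

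**How often the calendar triggers it**

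Assumptions, not taken from the documents: the medication has a partial start L days before first dose, it stopped 3 days before first dose, and first-dose dates are spread evenly over one 365-day year.

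- Month and year known: error if the start falls in the dosing month. Share = sum over the 12 months of max(0, days in month − L) / 365.
- Year only: error if the start falls in the dosing year. Share = (365 − L) / 365.

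| L (days) | Month and year known | Year only |
|---|---|---|
| 7 | 281/365 = 77.0% | 358/365 = 98.1% |
| 14 | 197/365 = 54.0% | 351/365 = 96.2% |
| 28 | 29/365 = 7.9% | 337/365 = 92.3% |
| 60 | 0% | 305/365 = 83.6% |
| 90 | 0% | 275/365 = 75.3% |
| 180 | 0% | 185/365 = 50.7% |

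These are shares among records that already have a partial start and a pre-dose stop. They are not shares of all medications. Year-only starts are the main exposure.

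**Procedures**

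The shells for Listings 16.2.4.5 and 16.2.4.6 show one date per ocular intervention, surgery or procedure and no stop date. If no stop date is recorded, the second condition of 8.3.1 cannot be met. Read literally, even a procedure dated only to an earlier year could then not be excluded.

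**The case against.** The strongest case against is that this is a drafting slip with narrow reach, and much of that case stands.

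- **Scope.** A reader might infer that any known pre-dose stop is overridden. It is not. Complete dates are outside the rule, and an earlier partial start with a pre-dose stop is excluded correctly.
- **Analysis consequences.** A reader might infer that a mislabelled prohibited therapy would trigger intercurrent event 3 or removal from the per-protocol set. The documents do not support this. SAP section 7.1 defines that event by initiation of prohibited rescue treatment or procedures during the 8-week treatment period. SAP sections 6.4 and 6.6 base per-protocol exclusion on major deviations settled at the blinded data review. Neither uses the 8.3.1 flag.
- **Visibility.** Listing 16.2.4.4 prints start and stop dates, so a careful reader can see that the therapy ended before dosing. The record also still meets the prior-medication definition in 9.5.1. The fault is an added concomitant count, not the loss of a prior one.
- **Botulinum toxin.** This is a weak example. Protocol section 9.6.1 bars it for 90 days before Screening, so in an eligible patient only a year-only start could trigger the rule. Serum tears are the better case.
- **Percentages.** They depend on assumed dates. Because criterion 4 looks back two weeks before Screening, the 7-day row fits therapy already in use poorly.
- **Missing start date in 9.5.2.** The clause names only a stop on or after the last dose. A drug of unknown start that stopped in mid-treatment is still concomitant under the general definition, so the clause is untidy and causes little harm.

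The plea that the rule is merely conservative does not stand. The adverse-event rule in SAP section 12.1 is described as worst case, yet it accepts a stop before first dose as sufficient.

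**Conclusion.** The rule is wrong as written, within a narrow scope. It misclassifies a medication when three things coincide: the start date is partial; the partial start falls in the same month as first dose (day missing) or the same year (day and month missing); and the known stop date is before first dose. Each such record contradicts the 9.5.2 definition.

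The consequence is descriptive: over-counting on the Concomitant pages of Table 14.1.4.1 and a wrong flag in Listing 16.2.4.4. The documents do not say how many start dates will be partial, so the number of affected records is unknown and could be zero. No effect on intercurrent event 3, the per-protocol set or the primary result is shown. The correction is worth making because the error is certain wherever the conditions are met and costs almost nothing to remove.

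**What to change.** 1. In SAP section 8.3.1, for both the missing-day and the missing-month rules, state that a medication with a partial start date is not concomitant if its stop date (full, or partial and unambiguously earlier) is before first study drug administration, regardless of the start date. Otherwise count it as concomitant unless its partial start is unambiguously after the last dose.
2. Do not simply replace 'and' with 'or'; row 5 of the worked dates shows what would be lost.
3. For interventions, surgeries and procedures recorded with a single date, classify on that date alone: not concomitant if the known month and year, or year, is before that of first dose.
4. As a minor tidy-up in section 9.5.2, for a missing start date, make the reference point for the stop date the first treatment administration instead of the last, to match the general definition.

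The cost is a few wording edits and a small change to the derivation of the flag. No new data are needed.

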8.4. Visit Windows

The allowed time windows between visits are detailed in Table 13, Appendix 1.

8.5. Pooling of Centres

For the efficacy endpoint analyses the sites are already pooled by region which is a randomisation stratum.

8.6. Subgroups

Subgroups for additional analyses, such as gender, NK stage, region, or other specific characteristics, may be defined at the time of the BDRM before DB lock and prior to unmasking.

9. Demographic, Other Baseline Characteristics and Medication

9.1. Patient Disposition and Withdrawals

Patient disposition will be summarised by treatment group and overall and will include the following:

- Number of patients screened
- Number of screen failures
- Number (%) of patients treated
- Number (%) of patients by region (at randomisation), country and site
- Number (%) of patients by disease stage (at randomisation)
- Number (%) of patients completing the study
- Number (%) of patients who discontinued treatment and/or study and reason(s) for discontinuation
- Number (%) in each patient population for analysis (the reasons for exclusion from the analysis populations will be listed)

All disposition data will be presented in by-patient listings.

9.2. Demographic and Other Baseline Characteristics

9.2.1. Demographics

Demographics and baseline characteristics will be presented by treatment group and overall. The following variables will be summarised using both continuous and categorical descriptive statistics based on the mITT and PP populations:

- Region (at randomisation)
- Country
- Disease stage (as reported at screening and at randomisation)
- Age (years)
- Sex
- Childbearing potential
- Race
- Ethnicity
- Iris color of the study eye
- Weight (kg)
- Height (cm)
- Alcohol status
- Smoking status

Additionally, all demographics and baseline characteristics will be listed for the enrolled population.

